9.5.2.2 Description of Procedures/Assessments Schedule

Refer to [Table 8](#) (for Phase 1b) and [Table 9](#) (for Phase 2) for the description and timing of each procedure and assessment in the Pretreatment and Treatment Phase and the Extension Phase, respectively.

9.5.3 Appropriateness of Measurements

All clinical assessments are standard measurements commonly used in studies involving subjects with solid tumors.

The safety assessments to be performed in this study, including hematology analyses, blood chemistry tests, urinalysis, and assessment of AEs, are standard evaluations to ensure subject safety.

9.5.4 Reporting of Serious Adverse Events, Pregnancy, and Events Associated with Special Situations

9.5.4.1 Reporting of Serious Adverse Events

All SERIOUS ADVERSE EVENTS, regardless of their relationship to study treatment, must be reported on a completed SAE form by email or fax as soon as possible but no later than 24 hours from the date the investigator becomes aware of the event.

Deaths and life-threatening events should be reported immediately by telephone. The immediate report should be followed up within 24 hours by emailing or faxing the completed SAE form.

Serious adverse events, regardless of causality assessment, must be collected through 90 days after the subject's last dose, or 30 days following the last dose if the subject initiates new anticancer therapy, whichever is earlier. All SAEs must be followed to resolution or, if resolution is unlikely, to stabilization. Any SAE judged by the investigator to be related to the study treatment or any protocol-required procedure should be reported to the sponsor regardless of the length of time that has passed since study completion.

The detailed contact information for reporting of SAEs is provided in the Investigator Study File.

For urgent safety issues, please ensure all appropriate medical care is administered to the subject and contact the appropriate study team member listed in the Investigator Study File.

It is very important that the SAE report form be filled out as completely as possible at the time of the initial report. This includes the investigator's assessment of causality.

Any follow-up information received on SAEs should be forwarded within 24 hours of its receipt. If the follow-up information changes the investigator's assessment of causality, this should also be noted on the follow-up SAE form.

Preliminary SAE reports should be followed as soon as possible by detailed descriptions including copies of hospital case reports, autopsy reports, and other documents requested by the sponsor.

The investigator must notify his/her IRB/IEC of the occurrence of the SAE in writing, if required by their institution. A copy of this communication must be forwarded to the sponsor to be filed in the sponsor's Trial Master File.

Eisai will provide a Safety Reporting Plan (SRP) for lenvatinib and pembrolizumab. The plan will address the following:

- Holder of the Global Safety Database
- Procedures and timelines for the processing of SAEs
- The distribution of expedited SAE reports
- Responsibility for submission to Health Authorities and notifications to investigators and the EC/IRB
- Adverse Events of Special Interest reports including pregnancy reports, and overdose
- Case closure
- SAE reconciliation
- Translation of source documents
- Schematic of work flow and timelines

9.5.4.2 Reporting of Pregnancy and Exposure to Study Drug Through Breastfeeding

Any pregnancy in which the estimated date of conception is either before the last visit or within 120 days of the last study treatment or 30 days following last study treatment if the subject initiates new anticancer therapy, whichever is earlier, must be reported. Also, any exposure to study drug through breastfeeding during study treatment or within 120 days of the last study treatment, or 30 days following the last study treatment if the subject initiates a new anticancer therapy, whichever is earlier, must be reported.

If an adverse outcome of a pregnancy is suspected to be related to study drug exposure, this should be reported regardless of the length of time that has passed since the exposure to study treatment.

A congenital anomaly, death during perinatal period, an induced abortion, or a spontaneous abortion are considered to be an SAE and should be reported in the same time frame and in the same format as all other SAEs (see Reporting of Serious Adverse Events [[Section 9.5.4.1](#)]).

Pregnancies or exposure to study drug through breastfeeding must be reported by fax or email as soon as possible but no later than 24 hours from the date the investigator becomes aware of the pregnancy. The contact information for the reporting of pregnancies and exposure to study drug through breastfeeding is provided in the Investigator Study File. The Pregnancy Report Form must be used for reporting. All pregnancies must be followed to outcome. The outcome of the pregnancy must be reported as soon as possible but no later than 24 hours from the date the investigator becomes aware of the outcome.

A subject who becomes pregnant must be withdrawn from the study

9.5.4.3 Reporting of Events Associated with Special Situations

9.5.4.3.1 REPORTING OF ADVERSE EVENTS ASSOCIATED WITH STUDY DRUG OVERDOSE, MISUSE, ABUSE, OR MEDICATION ERROR

Adverse events associated with study drug overdose, misuse, abuse, and medication error refer to AEs associated with uses of the study drug outside of that specified by the protocol. Overdose, misuse, abuse, and medication error are defined as follows:

Overdose	Accidental or intentional use of the study drug in an amount higher than the protocol-defined dose
Misuse	Intentional and inappropriate use of study drug not in accordance with the protocol
Abuse	Sporadic or persistent intentional excessive use of study drug accompanied by harmful physical or psychological effects
Medication error	Any unintentional event that causes or leads to inappropriate study drug use or subject harm while the study drug is in the control of site personnel or the subject.

All AEs associated with overdose, misuse, abuse, or medication error should be captured on the Adverse Event CRF and also reported using the procedures detailed in Reporting of Serious Adverse Events ([Section 9.5.4.1](#)) even if the AEs do not meet serious criteria. Abuse is always to be captured as an AE. If the AE associated with an overdose, misuse, abuse, or medication error does not meet serious criteria, it must still be reported using the SAE form and in an expedited manner but should be noted as nonserious on the SAE form and the Adverse Event CRF.

Note: Overdose for pembrolizumab is defined as a dose greater than 5 times the 200 mg dose.

9.5.4.4 Expedited Reporting

The sponsor must inform investigators and regulatory authorities of reportable events, in compliance with applicable regulatory requirements, on an expedited basis (ie, within

specific time frames). For this reason, it is imperative that sites provide complete SAE information in the manner described above.

9.5.4.5 Breaking the Blind

Not applicable.

9.5.4.6 Regulatory Reporting of Adverse Events

Adverse events will be reported by the sponsor or a third party acting on behalf of the sponsor to regulatory authorities in compliance with local and regional law and established guidance. The format of these reports will be dictated by the local and regional requirements.

All studies that are conducted within any European country will comply with European Good Clinical Practice Directive 2005/28/EC and Clinical Trial Directive 2001/20/EC. All suspected unexpected serious adverse reactions (SUSARs) will be reported, as required, to the competent authorities of all involved European member states.

9.5.5 Completion/Discontinuation of Subjects

A subject may elect to discontinue the study at any time for any reason. All subjects who discontinue the study are to complete the study's early discontinuation procedures indicated in the Schedule of Procedures/Assessments ([Table 8](#) and [Table 9](#)).

The investigator will promptly explain to the subject involved that the study will be discontinued for that subject and provide appropriate medical treatment and other necessary measures for the subject. A subject who has ceased to return for visits will be followed up by mail, phone, or other means to gather information such as the reason for failure to return, the status of treatment compliance, the presence or absence of AEs, and clinical courses of signs and symptoms.

Subjects who discontinue early from the study will be discontinued for 1 of these primary reasons: AE(s), lost to follow-up, subject choice, progression of disease, withdrawal of consent, pregnancy, study terminated by sponsor, or other. In addition to the primary reason, the subject may indicate 1 or more secondary reason(s) for discontinuation. Study disposition information will be collected on the Subject Disposition CRF.

For Phase 1b study, subjects who discontinue study treatment prior to completing the Treatment Phase for any reason other than a DLT will be replaced. Subjects who discontinue study treatment prior to completing the Phase 2 Treatment Phase for reasons such as lost to follow-up, subject choice, withdrawal of consent, and pregnancy may be replaced.

9.5.6 Abuse or Diversion of Study Drug

Not applicable.

9.5.7 Confirmation of Medical Care by Another Physician

The investigator will instruct subjects to inform site personnel when they are planning to receive medical care by another physician. At each visit, the investigator will ask the subject whether he/she has received medical care by another physician since the last visit or is planning to do so in the future. When the subject is going to receive medical care by another physician, the investigator, with the consent of the subject, will inform the other physician that the subject is participating in the clinical study.

9.6 Data Quality Assurance

This study will be organized, performed, and reported in compliance with the protocol, SOPs, working practice documents, and applicable regulations and guidelines. Site audits will be made periodically by the sponsor's or the CRO's qualified compliance auditing team, which is an independent function from the study team responsible for conduct of the study.

9.6.1 Data Collection

Data required by the protocol will be collected on the eCRFs and entered into a validated data management system that is compliant with all regulatory requirements. As defined by ICH guidelines, the CRF is a printed, optical, or electronic document designed to record all of the protocol-required information to be reported to the sponsor on each study subject.

Data collection on the CRF must follow the instructions described in the CCGs. The investigator has ultimate responsibility for the collection and reporting of all clinical data entered on the CRF. The investigator or designee as identified on Form FDA 1572 must sign the completed CRF to attest to its accuracy, authenticity, and completeness.

Completed, original CRFs are the sole property of Eisai and should not be made available in any form to third parties without written permission from Eisai, except for authorized representatives of Eisai or appropriate regulatory authorities.

9.6.2 Clinical Data Management

All software applications used in the collection of data will be properly validated following standard computer system validation that is compliant with all regulatory requirements. All data, both CRF and external data (eg, laboratory data), will be entered into a clinical system.

9.7 Statistical Methods

All statistical analyses will be performed by the sponsor or designee after the study is completed and the database is locked. Statistical analyses will be performed using SAS software or other validated statistical software as required. Details of the statistical analyses will be included in a separate statistical analysis plan (SAP).

9.7.1 Statistical and Analytical Plans

The statistical analyses of the core study data are described in this section. Further details of the analytical plan will be provided in the SAP, which will be finalized before database lock.

9.7.1.1 Study Endpoints

9.7.1.1.1 PRIMARY ENDPOINTS

Primary Efficacy Endpoint for Phase 1b:

The primary objective of Phase 1b is to determine the DLTs, MTD, and to establish the RP2D. The efficacy endpoints in Phase 1b will be summarized and listed by dose level based on the Safety Analysis Set. No statistical comparison will be performed.

Primary Efficacy Endpoint for Phase 2:

The primary objective of Phase 2 is to evaluate $ORR_{(Week\ 24)}$ in each of the cohorts using irRECIST. $ORR_{(Week\ 24)}$ is defined as the proportion of subjects who have best overall response (BOR) of irCR_(Week 24) or irPR_(Week 24) as of the Week 24 tumor assessment time point. The primary efficacy analysis for each cohort will be performed when all subjects in that cohort have completed 8 cycles of treatment, discontinued due to disease progression, developed unacceptable toxicity, withdrew consent, or the study is terminated by the sponsor.

9.7.1.1.2 SECONDARY ENDPOINTS (BOTH PHASE 1B AND PHASE 2)

The secondary efficacy endpoints will be ORR, PFS, OS, DCR, CBR, DOR, and durable SD rate (SD ≥ 23 weeks) by irRECIST as appropriate. The secondary efficacy endpoints are defined as follows.

- **ORR** is defined as the proportion of subjects who have BOR of irCR or irPR at the time of data cutoff.
- **PFS** is defined as the time from the first study dose date to the date of first documentation of confirmed disease progression or death (whichever occurs first). If a subject has not experienced disease progression or death, then the subject's data will be censored at the date of the last available tumor assessment.
- **OS** is measured from the start date of the treatment period until date of death from any cause. Subjects who are lost to follow-up and the subjects who are alive at the date of data cutoff will be censored at the date the subject was last known alive.
- **DCR** is defined as the proportion of subjects who have BOR of irCR or irPR or irSD (duration of irSD ≥ 5 weeks).
- **CBR** is defined as the proportion of subjects who have BOR of irCR or irPR or durable irSD (duration of irSD ≥ 23 weeks).
- **DOR** is defined as the time from the date the criteria are met for an irCR or irPR (whichever is recorded first) to the date the disease progression is objectively

documented. If a subject has no record of disease progression, then the subject's data will be censored at the last available tumor assessment.

- **Durable SD rate** is defined as the proportion of subjects whose BOR is irSD and the duration of irSD is ≥ 23 weeks.

Determination of the plasma PK profile of lenvatinib while subjects are receiving combination therapy also is a secondary endpoint.

9.7.1.1.3 EXPLORATORY ENDPOINTS

The exploratory endpoints include:

- Tumor response endpoints based on investigator assessment using modified RECIST 1.1
- Tumor response endpoints for the subjects in the endometrial and renal cell carcinoma analysis sets based on IIR assessments using irRECIST, modified RECIST 1.1, and RECIST v1.1
- To identify and explore blood and tumor biomarkers which correlate with clinical endpoints of this study including safety and efficacy

9.7.1.2 Definitions of Analysis Sets

Safety Analysis Set will include all subjects who received any amount of study drug. This will be the analysis set for all safety evaluations.

MTD Analysis Set will include all subjects who have completed C1 treatment of Phase 1b or discontinued early due to DLT. This will be the analysis set to determine MTD.

Full Analysis Set (Intent-to-Treat [ITT] Analysis Set) will include all subjects who entered the study treatment period. Efficacy analyses will primarily be based on the Full Analysis Set.

PK Analysis Set All the subjects who have received at least one dose of study drug (lenvatinib) and have evaluable concentration data.

Pharmacodynamic Analysis Set will include all subjects who have received at least one dose of study drug (lenvatinib or pembrolizumab) and have evaluable pharmacodynamic data.

Endometrial Carcinoma Analysis Set will include all EC subjects from Phase 1b and Phase 2.

Renal Cell Carcinoma Analysis Set will include all renal cell carcinoma subjects from Phase 1b and Phase 2.

Non-Small Cell Lung Cancer Analysis Set will include all NSCLC subjects from Phase 1b and Phase 2.

Melanoma Analysis Set will include all melanoma subjects from Phase 1b and Phase 2.

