If 0 of 3 subjects in a given dose level cohort experiences a DLT, then 7 more subjects will be enrolled into that dose level to confirm the MTD. If 1 of 3 subjects has a DLT, then 3

more subjects will be enrolled into that dose level for a total of 6 subjects. If only 1 of these 6 subjects has a DLT, then 4 more subjects will be enrolled into that dose level to confirm the MTD.

As shown in Figure 1, if 2 or more subjects at a dose level experience a DLT, then, following consultation with the PIs the study will proceed with enrollment in the next defined lower dose (Dose Level 2 or 3), with dose reduction of lenvatinib to 20 or 14 mg QD, respectively, in combination with 200 mg pembrolizumab Q3W.

For confirming the MTD, DLTs and intolerable toxicities (that cannot be managed with dose interruption and/or reduction) during the first cycle of treatment for the 10 evaluable subjects at that dose level will be assessed. The MTD will be confirmed if no more than 3 subjects experience DLTs during the first 3 weeks (Cycle 1) of treatment. If the MTD is not confirmed at a dose level, then enrollment will proceed to the next lower dose level. The sponsor and investigators will review all subjects' safety and clinical data to jointly determine the RP2D of the combination of lenvatinib with pembrolizumab.

If 2 or more subjects have a DLT in Dose Level 3, enrollment in the study will stop.

[figure not shown]

Figure 1 Phase 1b – Determination and Confirmation of the Maximum Tolerated Dose

DLT = dose limiting toxicity, IV = intravenous, MTD = maximum tolerated dose, PO = orally, Q3W – every 3 weeks

a: where DLTs are considered lenvatinib related.

A DLT is defined as any of the following:

- Any of the hematological or nonhematological toxicities noted in Table 1 considered to be at least possibly related to lenvatinib and/or pembrolizumab occurring during Cycle 1.
- Failure to administer $\geq 75\%$ of the planned dosage of lenvatinib as a result of treatment-related toxicity during Cycle 1.
- Subjects who discontinue treatment due to treatment-related toxicity.
- Greater than 2 week delay in starting Cycle 2 because of a treatment-related toxicity, even if the toxicity does not meet DLT criteria.

Table 1 Dose-Limiting Toxicities

Toxicity Category	Toxicity CTCAE Grade

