Hematologic	
 • Grade 4 neutropenia for ≥ 7 days • Grade 3 or Grade 4 febrile neutropenia^a • Thrombocytopenia $< 25,000/\text{mm}^3$ associated with bleeding and/or which requires platelet transfusion
Other nonhematologic toxicity	
 • Any other Grade 4 or a Grade 5 toxicity • Grade 3 toxicities lasting > 3 days excluding: 
 • Nausea, vomiting, and diarrhea controlled by medical intervention within 72 hours. • Grade 3 rash in the absence of desquamation, no mucosal involvement, does not require steroids, and resolves to Grade 1 by the next scheduled dose of pembrolizumab. • Grade 3 hypertension not able to be controlled by medication • Grade 3 or above gastrointestinal perforation • Grade 3 or above wound dehiscence requiring medical or surgical intervention • Any grade thromboembolic event
	Any Grade 3 nonhematologic laboratory value if: 
 • Medical intervention is required to treat the subject, or • The abnormality leads to hospitalization

ANC = absolute neutrophil count, CTCAE = Common Terminology Criteria for Adverse Events v4.03.

a. Febrile neutropenia Grade 3 or Grade 4:

Grade 3 is defined as $\text{ANC} < 1000/\text{mm}^3$ with a single temperature of $> 38.3^\circ\text{C}$ (101°F) or a sustained temperature of $\geq 38^\circ\text{C}$ (100.4°F) for more than one hour.

Grade 4 is defined as $\text{ANC} < 1000/\text{mm}^3$ with a single temperature of $> 38.3^\circ\text{C}$ (101°F) or a sustained temperature of $\geq 38^\circ\text{C}$ (100.4°F) for more than one hour, with life-threatening consequences and urgent intervention indicated

Only toxicities with a clear alternative explanation (eg, due to disease progression) or transient (≤ 72 hours), abnormal laboratory values without associated clinically significant signs or symptoms based on investigator determination, can be deemed a non-DLT.

All subjects enrolled in Phase 1b will be assessed for DLTs during the DLT assessment window of Cycle 1 (Treatment Phase). Subjects who discontinue study treatment prior to completing the Treatment Phase for any reason other than DLT will be replaced. Once they complete the Treatment Phase, each subject still receiving study treatment will transition into the Extension Phase. Tumor assessments will continue during the Extension Phase. As of

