9.4 Treatments

9.4.1 Treatments Administered

9.4.1.1 Lenvatinib

Lenvatinib will be administered with water orally once a day (with or without food) in 21-day cycles at approximately the same time each day. Treatment cycles will be counted continuously regardless of dose interruptions. On (D1) of each cycle, it will be administered approximately 1 hour after completion of pembrolizumab administration.

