5.2 Study Subjects

5.2.1 Definitions of Analysis Sets

The following analysis sets will be defined:

Safety Analysis Set will include all subjects who received any amount of study drug. This will be the analysis set for all safety evaluations.

Full Analysis Set (Intent-to-Treat [ITT] Analysis Set) will include all subjects who entered the study treatment period. Efficacy analyses will primarily be based on the Full Analysis Set. Efficacy analysis will use FAS and the specific cohort analysis set for EC, RCC and other cohorts.

Endometrial Carcinoma Analysis Set will include all endometrial carcinoma subjects from Phase 1b and Phase 2.

Renal Cell Carcinoma Analysis Set will include all renal cell carcinoma subjects from Phase 1b and Phase 2.

Non-Small Cell Lung Cancer Analysis Set will include all non-small cell lung cancer subjects from Phase 1b and Phase 2.

Melanoma Analysis Set will include all melanoma subjects from Phase 1b and Phase 2.

Pharmacokinetic (PK) Analysis Set will include all subjects who have received at least one dose of lenvatinib and have evaluable lenvatinib concentration data.

Pharmacodynamic (PD) Analysis Set will include all subjects who have received at least 1 dose of study drug (lenvatinib or pembrolizumab) and have evaluable pharmacodynamic data.

MTD Analysis Set will include all subjects who have completed cycle 1 treatment of Phase 1b or discontinued early due to DLT. This will be the analysis set to determine MTD.

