5.4.1 Primary Analysis for Phase 1b

The primary objective of Phase 1b is to determine the DLTs, MTD, and to establish the RP2D. The endpoint DLTs in Phase 1b will be summarized based on the MTD Analysis Set.

5.4.2 Primary Efficacy Analysis for Phase 2

The primary efficacy endpoint in Phase 2 is objective response rate as of Week 24 (ORR_(Week 24)) based on irRECIST. The primary efficacy analysis of ORR(Week 24) for each cohort may be performed based on the Full Analysis Set when all subjects in that cohort have completed 8 cycles of treatment, or discontinued early due to disease progression, unacceptable toxicity, consent withdrawn, or the study termination by the Sponsor. Estimated ORR_(Week 24) and the exact 95% confidence intervals using the method of Clopper–Pearson will be presented.

5.4.3 Secondary Efficacy Analyses for Both Phase 1b and Phase 2

The following secondary efficacy analyses will be performed.

Objective Response Rate (ORR): The ORR is the proportion of patients achieving a best overall response of confirmed PR or CR at the time of data cutoff. Subjects who do not have a tumor response assessment for any reason will be considered non-responders and will be included in the denominator when calculating the response rate. The count and percentage for the ORR will be summarized. ORR and corresponding 95% CI based on exact binomial distribution will be estimated for each treatment cohort.

Progression-Free Survival (PFS): The PFS is defined as the time from the first study dose date to the date of first documentation of confirmed PD using irRECIST or death (whichever occurs first). If a subject has not experienced disease progression or death, then the subject's

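### The Phase 1b MTD set depends on why a subject stopped, not on whether a DLT occurred, so an observed DLT can fall outside the primary analysis; separately, the DLT counting window does not reach the Cycle 2 delay criterion

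*Protocol*

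**What the plan says.** **Analysis set.** Protocol 9.7.1.2: "MTD Analysis Set will include all subjects who have completed C1 treatment of Phase 1b or discontinued early due to DLT". SAP 5.2.1 repeats the protocol definition: "MTD Analysis Set will include all subjects who have completed cycle 1 treatment of Phase 1b or discontinued early due to DLT". The protocol adds "This will be the analysis set to determine MTD", and SAP 5.4.1 says "The endpoint DLTs in Phase 1b will be summarized based on the MTD Analysis Set".

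**Replacement.** Protocol 9.1: "Subjects who discontinue study treatment prior to completing the Treatment Phase for any reason other than DLT will be replaced". The Synopsis, Protocol 9.5.5 and SAP 13.2 carry the same rule. For Phase 1b the Treatment Phase is Cycle 1.

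**What counts as a DLT.** Protocol 9.1 and SAP 13.2 list four routes:

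1. A tabulated toxicity, at least possibly related, in Cycle 1 (Protocol Table 1).
2. Less than 75% of planned lenvatinib given in Cycle 1 because of related toxicity.
3. Stopping treatment for related toxicity.
4. "Greater than 2 week delay in starting Cycle 2 because of a treatment-related toxicity, even if the toxicity does not meet DLT criteria".

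Only route 3 requires the subject to stop.

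**Counting window.** Protocol 9.1: "The MTD will be confirmed if no more than 3 subjects experience DLTs during the first 3 weeks (Cycle 1) of treatment". The paragraph on determining the MTD in the same section restricts assessment to DLTs per Table 1 in the first cycle. The Synopsis and SAP 3.2 keep the first-cycle limit without naming the table.

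**The concern.** The DLT count is the Phase 1b primary endpoint, and the dose chosen from it is the one given to all six Phase 2 cohorts. A set meant to determine an MTD should contain everyone who had a DLT, plus those observed through the window without one. Here the second entry condition is discontinuation caused by a DLT, which is not the same as having had a DLT. A subject can meet route 1 or 2, stay on treatment, and then leave Cycle 1 for an unrelated reason. On the text that subject is neither a completer nor a DLT discontinuation, so the DLT is not in the primary summary and a new subject takes the place.

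The window raises a different question. A subject with a delayed Cycle 2 has completed Cycle 1 and is inside the set. The difficulty is that the counting sentences stop before the delay can be seen, so the text does not say whether that DLT is counted.

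**Working it through.** **1. The plan's own size.** After 0 of 3 with a DLT, 7 more enrol: 3 + 7 = 10. After 1 of 3 and then 1 of 6, 4 more enrol: 6 + 4 = 10. With one to three dose levels, 1 × 10 = 10 to 3 × 10 = 30, as stated in Protocol 9.7.2. No alpha, power or DLT rate is given for Phase 1b.

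**2. A subject who falls through.** Suppose a thromboembolic event on Day 8 (any grade is a DLT in Table 1) for which treatment is not stopped, then withdrawal of consent on Day 15.

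| Test | Result |
|---|---|
| Had a protocol-defined DLT? | Yes, route 1 |
| Completed Cycle 1? | No |
| Discontinued because of a DLT? | No, withdrew consent |
| In the MTD set? | No |
| Replaced? | Yes |

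**3. Effect at the threshold.** Confirmation allows at most 3 DLT subjects among 10. If 4 of 11 treated subjects had a DLT, one of the four was replaced, and the replacement had none, the set shows 4 − 1 = 3 DLTs in 11 − 1 = 10 subjects. That is confirmed on the set and not confirmed if all four count.

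**4. Average effect, under assumptions.** Let p be the true DLT rate, q the share of DLT subjects who leave Cycle 1 for another reason, and w the share of other subjects who leave. None of these is in the documents.

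- Counted rate on the text as written: p(1−q) / [p(1−q) + (1−p)(1−w)].
- Counted rate with every DLT kept: p / [p + (1−p)(1−w)].
- Chance of confirming at counted rate r: (1−r)³·P(X₇ ≤ 3) + 3r(1−r)⁵·P(X₄ ≤ 2), where Xₙ is binomial(n, r).

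At r = 0.30 this is 0.343 × 0.874 + 0.1513 × 0.916 = 0.438. For p = 30%:

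| q | w | Counted rate, as written | Confirm, as written | Confirm, every DLT kept |
|---|---|---|---|---|
| 5% | 0 | 0.289 | 0.464 | 0.438 |
| 10% | 0 | 0.278 | 0.491 | 0.438 |
| 20% | 0 | 0.255 | 0.548 | 0.438 |
| 10% | 10% | 0.300 | 0.438 | 0.386 |

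The calculation applies the MTD set at every stage, including the 3- and 6-subject steps, where the protocol is not explicit. It therefore shows the full effect of a literal reading.

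**5. The window.** Planned Cycle 2 Day 1 is Day 22. A delay of more than 14 days is established only after Day 22 + 14 = Day 36. The confirmation count covers 21 days. Route 4 therefore always becomes visible at least two weeks after the stated count closes. Routes 2 to 4 also lie outside Table 1, the only source named in the MTD-determination paragraph of Protocol 9.1.

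**The case against.** **Other safeguards.** Protocol 9.1 says all enrolled Phase 1b subjects are assessed for DLTs, and that sponsor and investigators review all subjects' safety and clinical data to set the Phase 2 dose. SAP 5.6.2 describes weekly monitoring, joint declaration of DLTs and joint dose-level decisions. The event also remains in the Safety Analysis Set and the adverse event listings. This stands: the DLT would not vanish from the record, and practice may have been safer than the wording. But being assessed does not place a subject in the MTD set, and nothing restores the subject to the SAP 5.4.1 summary.

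**Narrowness.** Stopping for related toxicity is route 3, so those subjects stay in. Protocol 9.3.3 records contributing as well as primary reasons for stopping. Progression is an unlikely exit, since the first scheduled scan is at Week 6. This also stands.

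**Stronger readings a reader might infer:**

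- *That 2 of 6 becomes 1 of 6, with a 67% to 90% chance of a changed decision.* Protocol 9.1 triggers de-escalation on subjects at a dose level, without limiting them to the MTD set; SAP 3.2 refers to the six subjects. The text is ambiguous. The percentages are only 1 − 0.33 and 1 − 0.10, the chance that one replacement has no DLT once the narrow case has already happened. They are not a risk estimate.
- *That the rules always err toward too few DLTs.* The set also drops subjects who leave without a DLT. With q = w the counted rate equals p (last row of the table); it falls below p only when q > w. With every DLT kept, the counted rate rises to 0.3 / 0.93 = 0.323 at w = 10%. That is the price of never discarding an observed DLT.
- *That the delay criterion can never be met, because "Treatment cycles will be counted continuously regardless of dose interruptions".* The amendment history dates that sentence to Amendment 05 (22 Dec 2017), for numbering and tabulating cycles. The Phase 2 dose was already in Amendment 03 (26 Oct 2016). The sentence could not have affected the dose decision, and it concerns interruptions rather than a late start.

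**Conclusion.** The definition is wrong as written in both documents, and the window does not fit one of the protocol's own DLT criteria. Two separate mechanisms are involved and neither explains the other.

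The set gap is small in scope. It needs a DLT that did not end treatment, followed by exit from Cycle 1 for another reason. Where it occurs, one subject can move a dose level across the 3-of-10 threshold, provided the replacement has no DLT. Averaged over assumed exit rates of 5% to 20% among DLT subjects and none among others, the chance of confirming at a true 30% DLT rate rises from 0.438 to between 0.464 and 0.548. Those exit rates are illustrative.

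The documents do not show that any DLT subject was replaced or that any Cycle 2 delay was missed. Phase 1b is complete and the Phase 2 dose is set, so the point concerns correct definition and transparent reporting. It does not show that the dose decision was wrong.

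**What to change.** 1. **Analysis set** (Protocol 9.7.1.2, Synopsis, SAP 5.2.1): define the MTD set as all Phase 1b subjects who had a DLT, or who completed Cycle 1 without one.
2. **Replacement** (Protocol 9.1 and 9.5.5, Synopsis, SAP 13.2): align the wording, so that only subjects who leave Cycle 1 without having had a DLT are described as replaced.
3. **Window** (Protocol 9.1, Synopsis, SAP 3.2): reconcile the Table 1 and first-cycle restriction, the 3-week confirmation count and the Cycle 2 delay criterion, so that one stated window covers every listed DLT criterion. This review takes no position on any dose or dose rule.
4. **Reporting** (SAP 5.4.1 and 5.6.2): because Phase 1b is complete, present DLTs for all treated Phase 1b subjects by dose level, alongside the MTD-set summary. Identify any subject who had a DLT and was replaced, and any whose Cycle 2 start was delayed by more than 2 weeks for related toxicity.

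The cost is wording in two documents, one extra table, and a check of Phase 1b subjects who left Cycle 1 early or started Cycle 2 late. No new data are needed.
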